8. Have received no prior systemic therapy for advanced RCC.
9. Have undergone a partial nephroprotective or radical complete nephrectomy (and complete resection of solid, isolated, soft tissue metastatic lesion(s) in M1 NED participants) with negative surgical margins.
10. Must have undergone a nephrectomy and/or metastasectomy ≥ 28 days prior to signing informed consent and ≤ 12 weeks prior to randomization.
11. Must be tumor free as assessed by the investigator and validated by either CT or MRI scan of the brain and CAP and a bone scan ≤ 28 days from randomization. All baseline scans must be sent to the central imaging vendor and receipt must be confirmed prior to randomization.

12. Must have provided adequate tissue per the following:

- Nephrectomy only: tissue from nephrectomy (required).
- Synchronous M1 NED: tissue from nephrectomy (required) AND, metastasectomy tissue (if available).
- Metachronous M1 NED: tissue from metastasectomy (required) AND, nephrectomy tissue (if available).

Adequacy of the samples for biomarker analysis will be evaluated by a central laboratory.

Note: If submitting unstained cut slides, newly cut slides should be submitted to the testing laboratory within 14 days from the date the slides are cut (details pertaining to tumor tissue submission and guidelines for tissue adequacy can be found in the Procedure Manual).

13. Have an ECOG PS of 0 or 1.

14. Specimens must be collected within 10 days prior to randomization. Have adequate organ function as defined in the following table:

Table 3 Adequate Organ Function Laboratory Values

System	Laboratory Value
Hematological	
Absolute neutrophil count (ANC)	≥1500/μL
Platelets	≥100 000/μL
Hemoglobin	≥9.0 g/dL or ≥5.6 mmol/L ^a
Renal	
Creatinine OR Measured or calculated ^b creatinine clearance (GFR can also be used in place of creatinine or CrCl)	≤1.5 × ULN OR ≥30 mL/min for participants with creatinine levels >1.5 × institutional ULN
Hepatic	
Total bilirubin	≤1.5 ×ULN OR direct bilirubin ≤ULN for participants with total bilirubin levels >1.5 × ULN
AST (SGOT) and ALT (SGPT)	≤2.5 × ULN
Coagulation	
International normalized ratio (INR) OR prothrombin time (PT)	≤1.5 × ULN unless participant is receiving anticoagulant therapy as long as INR or PT is within therapeutic range of intended use of anticoagulants

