10.6.2 Statistical Methods for Safety Analyses

Safety and tolerability will be assessed by clinical review of all relevant parameters including AEs and laboratory tests.

Tiered Approach

The analysis of safety results will follow a tiered approach (Table 12). The tiers differ with respect to the analyses that will be performed. Safety parameters or adverse experiences of special interest that are identified a priori constitute "Tier 1" safety endpoints that will be subject to inferential testing for statistical significance with p values and 95% CI provided for between-group comparisons. Other safety parameters will be considered Tier 2 or Tier 3. There is no expectation of enhanced safety signal in this adjuvant study other than safety signals of which we are already aware from past studies. Participants do not have tumor burden and their existing safety profile might be less intensive. Hence, we do not expect any new safety signals. Therefore there are no events of interest that will be analyzed as Tier 1 safety endpoints in this study.

Tier 2 parameters will be assessed via point estimates with 95% CIs provided for between-group comparisons; only point estimates by treatment group are provided for Tier 3 safety parameters.

AEs (specific terms as well as system organ class terms) will be classified as belonging to "Tier 2" or "Tier 3," based on the number of events observed. Membership in Tier 2 requires that at least 10% of the subjects in any treatment group exhibit the event; all other AEs and predefined limits of change will belong to Tier 3.

The threshold of at least 10% of subjects with events was chosen because the incidence rate would allow meaningful statistical assessments; events reported in less frequent than 10% of subjects would obscure the assessment of overall safety profile and add little to the meaningful interpretation. Because many 95% CIs may be provided without adjustment for multiplicity, the CIs should be regarded as a helpful descriptive measure to be used in review, not a formal method for assessing the statistical significance of the between-group differences in AEs and predefined limits of change.

Continuous measures such as changes from baseline in laboratory values that are not prespecified as Tier 1 safety parameters will be considered Tier 3 safety parameters. Summary statistics for baseline, on-treatment, and change from baseline values will be provided by treatment group in table format.

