In addition, the broad clinical and laboratory AE categories consisting of the percentage of participants with Grade 3-5 AE (incidence $\geq 5\%$ of subjects in one of the treatment groups) and SAE (incidence $\geq 5\%$ of subjects in one of the treatment groups) will be considered Tier 2 endpoints.

The threshold of at least 5% of subjects with events was chosen for Tier 2 Grade 3-5 AEs and SAEs because the incidence rate would allow meaningful statistical assessments; those AEs are expected to happen less frequent than specific AEs/SOCs, but important for overall safety profile assessment.

The broad clinical and laboratory AE categories consisting of the percentage of subjects with any AE, any Grade 3-5 AE, any SAE, any drug-related AE, any AE that is both drug-related and Grade 3-5, any AE that is both serious and drug-related, dose modification due to AE, discontinuation due to an AE, death, and specific AEs or SOC with incidence $< 10\%$ of subjects in all of the treatment groups will be considered Tier 3 endpoints.

Note that 95% CIs will be provided for between-treatment differences in the percentage of participants with Tier 2 events; these analyses will be performed using the Miettinen and Nurminen method, an unconditional, asymptotic method.

Table 12 Analysis Strategy for Safety Parameters

Safety Tier	Safety Endpoint	95% CI for Treatment Comparison	Descriptive Statistics
Tier 2	Specific Serious AE (incidence $\geq 5\%$ of subjects in one of the treatment groups)	X	X
	Specific Grade 3-5 AE (incidence $\geq 5\%$ of subjects in one of the treatment groups)	X	X
	Specific AEs or SOCs (incidence $\geq 10\%$ of subjects in one of the treatment groups)	X	X
Tier 3	Any AE		X
	Any Serious AE		X
	Any Grade 3-5 AE		X
	Any drug-related AE		X
	Any Serious and Drug-related AE		X
	Any Grade 3-5 and Drug-related AE		X
	Dose Interruption due to AE		X
	Discontinuation due to AE		X
	Death		X
	Specific AEs or SOCs (incidence $< 10\%$ of subjects in all of the treatment groups)		X
	Change from Baseline Results (Labs, ECGs, Vital Signs)		X

Abbreviations: AE = adverse event; CI = confidence interval; ECG = electrocardiogram; PDLC = predefined limit of change; SOC = system organ class.

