3.6.2 Statistical Methods for Safety Analyses

Safety and tolerability will be assessed by clinical review of all relevant parameters including AEs, laboratory tests.

Tiered Approach

The analysis of safety results will follow a tiered approach (Table 3). The tiers differ with respect to the analyses that will be performed. Safety parameters or adverse experiences of special interest that are identified a priori constitute “Tier 1” safety endpoints that will be subject to inferential testing for statistical significance with p values and 95% CI provided for between-group comparisons. Other safety parameters will be considered Tier 2 or Tier 3. There is no expectation of enhanced safety signal in this adjuvant study other than safety signals of which we are already aware from past studies. Participants do not have tumor burden and their existing safety profile might be less intensive. Hence, we do not expect any new safety signals. Therefore there are no events of interest that will be analyzed as Tier 1 safety endpoints in this study.

Tier 2 parameters will be assessed via point estimates with 95% CIs provided for between-group comparisons; only point estimates by treatment group are provided for Tier 3 safety parameters.

Tier 2 Events

Tier 2 parameters will be assessed via point estimates with 95% CIs provided for differences in the proportion of participants with events using the Miettinen and Nurminen method, an unconditional, asymptotic method [3].

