Membership in Tier 2 requires that at least 10% of participants in any treatment group exhibit the event; all other AEs and predefined limits of change will belong to Tier 3. The threshold of at least 10% of participants was chosen for Tier 2 events because the population enrolled in this study is in critical condition and usually experiences various AEs of similar types regardless of treatment; events reported less frequently than 10% of participants would obscure the assessment of the overall safety profile and add little to the interpretation of potentially meaningful treatment differences. In addition, Grade 3 to 5 AEs ($\geq 5\%$ of participants in 1 of the treatment groups) and SAEs ($\geq 5\%$ of participants in 1 of the treatment groups) will be considered Tier 2 endpoints. Because many 95% CIs may be provided without adjustment for multiplicity, the CIs should be regarded as a helpful descriptive measure to be used in safety review, not as a formal method for assessing the statistical significance of the between-group differences.

Tier 3 Events

Safety endpoints that are not Tier 1 or 2 events are considered Tier 3 events. The broad AE categories consisting of the proportion of participants with any AE, a drug related AE, a serious AE, an AE which is both drug-related and serious, a Grade 3-5 AE, a drug-related Grade 3-5 AE, and discontinuation due to an AE will be considered Tier 3 endpoints. Only point estimates by treatment group are provided for Tier 3 safety parameters.

Continuous measures such as changes from baseline in laboratory that are not pre-specified as Tier-1 endpoints will be considered Tier 3 safety parameters. Summary statistics for baseline, on-treatment, and change from baseline values will be provided by treatment group in table format.

Table 3 Analysis Strategy for Safety Parameters

Safety Tier	Safety Endpoint	95% CI for Treatment Comparison	Descriptive Statistics
Tier 2	Grade 3-5 AE (incidence $\geq 5\%$ of participants in one of the treatment groups)	X	X
	Serious AE (incidence $\geq 5\%$ of participants in one of the treatment groups)	X	X
	AEs (incidence $\geq 10\%$ of participants in one of the treatment groups)	X	X
Tier 3	Any AE		X
	Any Grade 3-5 AE		X
	Any Serious AE		X
	Any Drug-Related AE		X
	Any Serious and Drug-Related AE		X
	Any Grade 3-5 and Drug-Related AE		X
	Discontinuation due to AE		X
	Dose Interruption due to AE		X
	Death		X

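### The sSAP's stated reason for the 10% Tier 2 cut-off does not fit this population and, separately, immune-related AEs below the Tier 2 cut-offs get no between-arm difference or CI

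*Combined protocol and SAP*

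**What the plan says.** **Cut-offs.** sSAP 3.6.2: "Membership in Tier 2 requires that at least 10% of participants in any treatment group exhibit the event". Grade 3-5 AEs and serious AEs enter Tier 2 at a lower level, 5% "of participants in 1 of the treatment groups) will be considered Tier 2 endpoints". Protocol 10.6.2 has the same two levels. Tier 2 events get a between-arm difference with a Miettinen-Nurminen 95% CI. Tier 3 events get per-arm point estimates only.

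**Reasons for the 10% level.** The sSAP gives two. The first is that it was chosen "because the population enrolled in this study is in critical condition and usually experiences various AEs of similar types regardless of treatment". The second is that "events reported less frequently than 10% of participants would obscure the assessment of the overall safety profile". Protocol 10.6.2 shares the second ("events reported in less frequent than 10% of subjects would obscure the assessment of overall safety profile"), but its other reason is that a 10% incidence permits a meaningful statistical assessment. It says nothing about how ill the participants are. For the lower level it says "The threshold of at least 5% of subjects with events was chosen for Tier 2 Grade 3-5 AEs and SAEs", and again cites meaningful assessment.

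**Tier 1.** Both documents reserve Tier 1 for safety events of special interest named in advance, then name none, because no signals are expected beyond those already known from earlier studies.

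**Immune-related events.** Protocol 7.2.1 (Table 5) lists the immune-related categories associated with pembrolizumab. The events of clinical interest in protocol 9.3.7 are only overdose and a liver-laboratory rule. Neither protocol 10.6.2 nor sSAP 3.6.2 specifies an immune-related AE analysis.

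**The concern.** There are two separate problems.

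The first is a factual one in the sSAP. A safety-reporting rule is explained by a severely ill population whose adverse events look alike on either treatment. This is an adjuvant trial in resected, tumor-free participants treated as outpatients, where a difference from placebo in adverse events is to be expected.

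The second is a gap in what the plan will report. A listed secondary objective is to compare safety and tolerability between the arms. In people with no visible disease, the excess of immune-related events over placebo is a main harm to weigh against any DFS gain. The plan decides by frequency alone whether that excess is given as an estimate with its uncertainty, although the event types of interest are known well enough to have their own table in the protocol.

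**Working it through.** **Step 1: the rationale against the rest of the documents.** No arithmetic applies here.

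| Place | What it says about the population or the cut-off |
|---|---|
| sSAP 3.6.2, Tier 2 Events | 10% chosen "because the population enrolled in this study is in critical condition and usually experiences various AEs of similar types regardless of treatment" |
| sSAP 3.6.2, Tiered Approach | "Participants do not have tumor burden and their existing safety profile might be less intensive" |
| Protocol 6.1 | tumor free at baseline per investigator; "Have an ECOG PS of 0 or 1" |
| Protocol 7.1 | all trial treatment is given to outpatients |
| Protocol 10.6.2 | same 10% level, different reason, no reference to severity of illness |

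The first row cannot be reconciled with the next three.

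**Step 2: the size of the gap.** The plan states no figure to reproduce. Inputs: 990 participants (sSAP 3.9, protocol 10.9) and 1:1 allocation, so 990 / 2 = 495 per arm, taking all randomized as treated.

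- Any grade: 0.10 × 495 = 49.5, so at least 50 participants in one arm.
- Grade 3-5 or serious: 0.05 × 495 = 24.75, so at least 25 in one arm.

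With the originally planned 950 (475 per arm) the counts are 48 and 24. At 495 per arm, a term with up to 49 any-grade cases in each arm, and up to 24 in each arm both as Grade 3-5 and as serious, gets no between-arm CI.

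**Step 3: would an interval below the cut-offs be informative?** The plan's own method was used. For a risk difference d, the Miettinen-Nurminen limits solve

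(p1 − p2 − d)² / V(d) = 1.96², with V(d) = [r1(1 − r1)/n1 + r2(1 − r2)/n2] × N/(N − 1),

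where r1 = r2 + d, r1 and r2 are the maximum-likelihood rates under that constraint, n1 = n2 = 495 and N = 990.

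Worked example, 24 vs 2, lower limit: p1 − p2 = 22/495 = 0.0444. At d = 0.0268 the constrained rates are r2 = 0.0072 and r1 = 0.0340, which gives √V = 0.0090 and (0.0444 − 0.0268)/0.0090 ≈ 1.96.

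The counts below are assumptions, because the documents give no expected immune-related AE rates.

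| Counts per 495 | Rates | Difference (points) | 95% CI (points) |
|---|---|---|---|
| 49 vs 10 (any grade) | 9.9% vs 2.0% | 7.9 | 5.1 to 11.0 |
| 49 vs 25 (any grade) | 9.9% vs 5.1% | 4.8 | 1.6 to 8.2 |
| 24 vs 2 (Grade 3-5 or serious) | 4.8% vs 0.4% | 4.4 | 2.7 to 6.8 |
| 24 vs 10 (Grade 3-5 or serious) | 4.8% vs 2.0% | 2.8 | 0.6 to 5.3 |
| 10 vs 1 | 2.0% vs 0.2% | 1.8 | 0.6 to 3.5 |
| 4 vs 1 | 0.8% vs 0.2% | 0.6 | −0.4 to 1.9 |

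The first five rows bound the excess usefully and none would be produced under the plan. The last row shows that at very low counts the interval settles little about whether there is an excess, though it still limits its size.

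**Step 4: does anything else fill the gap?** Tier 1 is empty, the events of clinical interest do not cover the Table 5 categories, and the sSAP's exposure-adjusted incidence and AE frequency by time period are both optional.

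**The case against.** The case for the plan is substantial.

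- **The comparison is not confined to events at 10% or more.** A reader might infer that from the any-grade sentence alone. Both documents also admit Grade 3-5 and serious AEs at 5%. This stands and sets the scope of the point.
- **The faulty sentence does not drive the rule.** A reader might infer that the misdescribed population is why rarer immune-related events go uncompared. The sSAP gives a second reason in the same sentence, and the protocol sets the same level without the faulty one. Removing the phrase would change no analysis. This also stands.
- **The protocol's reason is not refuted by the intervals above.** It says that 10% permits meaningful assessment, not that nothing lower does, and it uses the same argument for 5%. Its case against going lower is clarity of the overall profile, which is a judgement. It would be wrong to call it a numerical error.
- **A lower floor for all terms is not supported.** One might point to 4 vs 0, where the interval is 0.03 to 2.06 points. One placebo event moves it to −0.40 to 1.88, and Fisher's exact two-sided p for 4 vs 0 is 0.12. Applied to every AE term, such a floor would create the clutter that the plan wants to avoid.
- **The data are not lost.** Per-arm percentages are reported, so a reader can derive the difference and CI, and the eDMC reviews safety periodically. What is missing is the prespecified estimate.
- **The plan explains its empty Tier 1** by the absence of expected new signals. That is arguable, but known signals are the ones that can be listed in advance, and Table 5 already lists them.

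**Conclusion.** The point holds in two limited parts.

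1. The sSAP's population rationale for the 10% cut-off is wrong for this trial. It contradicts its own section and the eligibility criteria, and it differs from the protocol's rationale. This is a minor wording error with no effect on any analysis.
2. Independently of that wording, immune-related AE terms with fewer than 50 any-grade cases and fewer than 25 Grade 3-5 or serious cases in both arms are reported without a between-arm difference or CI. At about 495 per arm such an interval can be informative.

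The second part assumes that nearly all 990 randomized participants are treated, and it uses illustrative counts. Which Table 5 events would fall below the cut-offs cannot be known from the documents. A reader might infer that the plan conceals these harms or removes the randomized comparison. It does neither, since the rates are shown by arm. The primary DFS inference is not affected. This is a cheap improvement to how harm is quantified, not a flaw that undermines the trial.

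**What to change.** - **sSAP 3.6.2:** delete the clause about the population's condition. The protocol's rationale can take its place.
- **sSAP 3.6.2 and protocol 10.6.2:** prespecify as AEs of special interest the immune-related categories of protocol Table 5, in that table's own terms. This includes hyperthyroidism and hypothyroidism, and uses AST/ALT elevation or increased bilirubin rather than hepatitis. Add infusion reactions. For each, report the between-arm difference with a Miettinen-Nurminen 95% CI, for any grade and for Grade 3-5 or serious events, whatever the incidence.
- **Labelling:** both documents currently define special-interest events as Tier 1 with p values. State that these intervals are descriptive, without p values, for instance by placing the categories in Tier 2 by name.
- **Unchanged:** keep the 10% and 5% cut-offs for all other AE terms.

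**Cost.** Text edits, a fixed list of terms for each category, and extra table rows; no new data. With the nine named Table 5 categories plus infusion reactions, and Grade 3-5 and serious shown separately, this is at most (9 + 1) × 3 = 30 intervals. The downside is more unadjusted CIs, which both documents already treat as descriptive. The list should be fixed before unblinding, so that it is not open to selection afterwards.

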3.3 HYPOTHESES/ESTIMATION

Objective/Hypothesis	Endpoint(s)
Primary	

 Objective: To compare DFS as assessed by the investigator for participants treated with pembrolizumab versus those receiving placebo Hypothesis: Pembrolizumab is superior to placebo with respect to DFS 	
 DFS as assessed by the investigator: time from randomization to the first documented local recurrence, or occurrence of distant kidney cancer metastasis(es), or death due to any cause, whichever occurs first.
Secondary	
Key Secondary	

 Objective: To compare OS for participants treated with pembrolizumab versus those receiving placebo Hypothesis: Pembrolizumab is superior to placebo with respect to OS 	
 OS: time from randomization to death due to any cause.
Other Secondary	

 To compare the safety and tolerability profiles for participants treated with pembrolizumab versus those receiving placebo 	
 Adverse events (AEs), serious AEs (SAEs), AEs leading to discontinuation, deaths, laboratory values, and vital signs

 To compare measures of disease recurrence-specific survival (DRSS), as assessed by the investigator, in participants treated with pembrolizumab versus those receiving placebo 	
 DRSS1 as assessed by the investigator: time from randomization to the first documented local recurrence of RCC. DRSS2 as assessed by the investigator: time from randomization to the first documented local recurrence with visceral lesion or occurrence of distant

Objective/Hypothesis	Endpoint(s)
	kidney cancer metastasis(es) with visceral lesion, whichever occurs first.

 To compare event-free survival (EFS) as assessed by the blinded independent radiology review for participants treated with pembrolizumab versus those receiving placebo 	
 EFS as assessed by the blinded independent radiology review (BICR): time from randomization to the first documented local recurrence or occurrence of distant kidney cancer metastasis(es) among participants disease free at baseline (M0/M1-NED) by BICR; or disease progression among participants with baseline disease (M1) by BICR, or death due to any cause, whichever occurs first.

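### The overall safety contrasts have no prespecified between-arm interval, and the protocol and sSAP wording of the safety tiers is not consistent

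*Combined protocol and SAP*

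**What the plan says.** The objectives (protocol section 4, sSAP section 3.3) include "To compare the safety and tolerability profiles for participants treated with pembrolizumab versus those receiving placebo". The listed endpoints are AEs, SAEs, AEs leading to discontinuation, deaths, laboratory values and vital signs. No safety hypothesis is attached.

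Tier 1 is empty by design. For Tier 2 the sSAP gives "95% CIs provided for differences in the proportion of participants with events using the Miettinen and Nurminen method". Tier 2 covers AEs reaching 10% in an arm, and Grade 3-5 AEs and SAEs reaching 5%. For Tier 3, sSAP section 3.6.2 ends its list of overall categories with "discontinuation due to an AE will be considered Tier 3 endpoints. Only point estimates by treatment group are provided for Tier 3 safety parameters". Protocol Table 12 and sSAP Table 3 agree: the treatment-comparison CI column is blank for every overall row.

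The protocol narrative in section 10.6.2 is less tidy. One paragraph describes "the broad clinical and laboratory AE categories consisting of the percentage of participants with Grade 3-5 AE (incidence" at least 5%, adds SAEs on the same terms, and closes with "of subjects in one of the treatment groups) will be considered Tier 2 endpoints". A later paragraph lists any Grade 3-5 AE and any SAE, together with "dose modification due to AE, discontinuation due to an AE, death, and specific AEs or SOC with incidence" below 10%, as Tier 3.

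The sSAP explains its 10% cut-off "because the population enrolled in this study is in critical condition and usually experiences various AEs of similar types regardless of treatment". Earlier in the same section it says "Participants do not have tumor burden and their existing safety profile might be less intensive".

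**The concern.** The control is placebo and participants enter tumor-free, so benefit-risk depends heavily on the overall rates of serious and severe events and of stopping treatment because of an AE. Protocol section 5.4 itself assesses an earlier adjuvant trial on such contrasts. Under the tier rule, a common single AE term receives an interval for the arm difference, while the overall SAE and Grade 3-5 rates do not.

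The double placement has a practical effect. If the overall Grade 3-5 or SAE rate reaches 5% in either arm, one protocol paragraph read literally calls for an interval and another does not. The programmer then has to choose, possibly after seeing data.

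**Working it through.** **Stated figure.** The documents give no power, precision or sample size for any safety comparison, so there is nothing to reproduce. The check is a comparison of texts, followed by an illustration of what the missing intervals would show.

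**Texts side by side.**

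| Source | Grade 3-5 AE and SAE in Tier 2 | Grade 3-5 AE and SAE in Tier 3 |
|---|---|---|
| Protocol 10.6.2 narrative | 'Broad' categories at 5% or more | 'Any' |
| Protocol Table 12 | 'Specific' events at 5% or more | 'Any' |
| sSAP 3.6.2 narrative | Grade 3-5 AEs and SAEs at 5% or more, neither 'broad' nor 'specific' | Broad categories: a Grade 3-5 AE, a serious AE |
| sSAP Table 3 | Same rows as Table 12 but without 'Specific' | 'Any' |

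Table 12 shows the intended split: single terms in Tier 2, overall rates in Tier 3. The protocol narrative departs from it. Its reason for the 5% threshold contrasts these events with specific AEs and SOCs, so it does not settle the reading. The sSAP drops the word that would.

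**Illustration.** Inputs:
- n per arm = 990/2 = 495, from the total used in the power section with 1:1 allocation. The treated population may be slightly smaller.
- Rates from the sunitinib trial cited in protocol section 5.4: SAEs 21.9% and 17.1%; discontinuations due to AE 28.1% and 5.6%. These belong to a different drug and are assumptions here.

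Counts:
- SAEs: 0.219 × 495 = 108.4, taken as 108; 0.171 × 495 = 84.6, taken as 85.
- Discontinuations: 0.281 × 495 = 139.1, taken as 139; 0.056 × 495 = 27.7, taken as 28.

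The Miettinen-Nurminen limits are the values d at which

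z(d) = (p1 − p2 − d) / √{[r1(1 − r1)/n1 + r2(1 − r2)/n2] × N/(N − 1)}

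equals ±1.96. Here r1 and r2 are the maximum-likelihood rates under the constraint r1 − r2 = d, and N = n1 + n2 = 990.

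| Contrast (495 per arm) | Difference, points | 95% CI |
|---|---|---|
| SAE, 108 vs 85 | 4.6 | -0.3 to 9.6 |
| Discontinuation, 139 vs 28 | 22.4 | 18.0 to 26.9 |
| Assumed 30% vs 20%, 148 vs 99 | 9.9 | 4.5 to 15.2 |
| Assumed 20% in both, 99 vs 99 | 0.0 | -5.0 to 5.0 |
| Assumed 5% in both, 25 vs 25 | 0.0 | -2.8 to 2.8 |

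With 950/2 = 475 per arm the SAE contrast becomes 104 vs 81: 4.8 points, -0.2 to 9.9. No limit in the table moves by more than about 0.3 points.

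The protocol calls 21.9% and 17.1% similar. In a trial of this size those rates would be compatible with no excess and with an excess of almost 10 points. Both SAE rates also exceed 5%, so with rates of that order the tier conflict would arise in practice.

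**The case against.** The strongest reply is that little is lost. The objective carries no hypothesis and safety is assessed by clinical review. By-arm rates are reported for every overall category, and anyone can compute an interval from those counts. Tier 2 supplies between-arm intervals for common AEs and for Grade 3-5 AEs and SAEs at 5% or more. The sSAP also allows exposure-adjusted incidence, AE frequency by period and time to first Grade 3-5 AE. Table 12 resolves the tier conflict for a careful reader. The protocol itself discusses the sunitinib trial with bare percentages.

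Most of this stands, and it rules out several stronger readings:
- A reader might infer that the safety objective goes unanswered. It does not: by-arm rates answer it descriptively, and only the precision of the main contrasts is not prespecified.
- A reader might infer from the blank CI cell for death that mortality has no between-arm interval. All-cause death is the OS endpoint, with a stratified hazard ratio and 95% CI in the ITT population.
- A reader might infer that most immune-related events will fall below the thresholds and so escape comparison. The documents give no incidence for them. Protocol Table 5 is a management guide with an open-ended last category, so it is not a definition for a pooled analysis row.

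The reply does not explain why single terms merit an interval and the overall rates do not. That an interval can be derived later is also a weak reason to leave it out of a prespecified table whose method is already fixed.

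**Conclusion.** The point holds as a modest, inexpensive improvement. Neither plan prespecifies a between-arm interval for the eight overall safety rows other than death. The protocol's Tier 2 sentence disagrees with its own Table 12, and the sSAP Tier 2 sentence and table rows omit the qualifier that would make the split clear. The 'critical condition' rationale does not fit participants the same section describes as free of tumor burden.

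On size: at about 495 per arm, the unreported uncertainty is roughly ±5 points when both arms are near 20%, and ±2.8 points when both are near 5%. These figures rest on assumed rates and on nearly all randomized participants being treated; they are not forecasts for pembrolizumab. The tier conflict matters only if an overall rate reaches 5% in an arm. No efficacy conclusion, error rate or data collection is affected.

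**What to change.** 1. In protocol Table 12 and sSAP Table 3, mark the treatment-comparison CI column for eight rows: any AE; any Grade 3-5 AE; any serious AE; any drug-related AE; serious and drug-related; Grade 3-5 and drug-related; dose interruption due to AE; discontinuation due to AE. Use the Miettinen-Nurminen interval and label it descriptive and unadjusted, as for Tier 2. Amend the Tier 3 sentences that now limit reporting to by-arm estimates.
2. In the protocol Tier 2 sentence, replace the reference to broad categories with specific Grade 3-5 AEs and specific SAEs. Keep the sentence: it is the narrative basis for the 5% rule.
3. Insert 'specific' in the sSAP Tier 2 sentence and in the Tier 2 rows of sSAP Table 3.
4. Replace the sSAP's 'critical condition' rationale with the protocol's reason for the 10% threshold, that such an incidence allows a meaningful statistical assessment.

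The cost is wording plus eight intervals from counts already tabulated. Protocol section 10 routes changes to nonconfirmatory analyses, made before any analysis is conducted, through the sSAP. The added intervals can go there, with the protocol text aligned at its next amendment. The downside is a few more unadjusted descriptive intervals.
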